11.5 Salivary Biobanking

The remaining saliva will be biobanked in the -80 freezer in the [name] lab in a secure location. Future clinical studies on the biobanked may include investigations in the microbiome or cytokines.

11.6 Ultrasound Imaging Assessment

Salivary gland size will be measured by ultrasound⁴⁵. Ultrasound imaging is a non-ionizing, noninvasive imaging modality that can be quickly obtained in a standard exam room. Three-dimensional (3D) Bmode data sets will be acquired for gland volume measurements and characterization of the gland.

The lower outline of the gland will be used to define the distal (relative to the ultrasound probe) end of the gland. This assessment is necessary to provide a 3D volume. In a series of six patients imaged as part of a pilot study, determination of 3D gland volume was possible in all patients. Rarely the lower, or distal aspect of the gland can be difficult to visualize, particularly after radiation⁴⁵. Under this circumstance, 2D measurements will be employed to estimate gland volume for the study patient. The salivary gland volumes will be used to determine if gland volume increases after MSC administration. Additionally, the stiffness of the salivary glands will be measured by shear wave velocity. Acoustic radiation force impulse imaging is a type of ultrasound technique employed to measure elasticity and fibrosis of salivary glands via shear wave velocity. Stiffness, or fibrosis, will be assessed at baseline and after MSC injection. Acoustic radiation force impulse imaging is used in multiple salivary gland conditions including Sjogren's syndrome to measure fibrosis^{46,47}. The evaluators will be blinded to the time point of evaluation (pre- or post- MSC injection).

Ultrasound assessment of salivary glands will be done at the baseline, 3-month, 6-month, and 12-month follow-up visits.

11.7 Biobanking of Blood Sample

Biobanking of participant blood will occur at a baseline visit or the day of the bone marrow aspiration, and at the 1 (for those seen at 1 month), 3, 6, 12, and 24 month visits. Approximately 3 mL of blood will be placed into an EDTA tube which will be transported to the [name] lab, in WIMR where it will be stored in a secure freezer in a secure location. Future clinical studies on the biobanked blood may include measuring inflammatory cytokines or other immune markers.

12.0 DATA COLLECTION, HANDLING, SHARING, AND RECORD KEEPING

12.1 Data Collection

Data Collection Forms

Standardized data collection forms (e.g., source documents, case report forms, standardized assessment forms, etc.) are used to ensure data collected are consistent and compliant with the protocol and IRB application.

Data collection is the responsibility of study team members under the supervision of the Principal Investigator (PI). The PI is responsible for ensuring the accuracy, completeness, legibility, and timeliness of the recorded and reported data.

All data collection forms must be completed in a legible manner; any missing data will be explained. Data entry errors will be corrected with a single line through the incorrect entry and the correct data is entered above/near the correction. All changes will be initialed and dated.

Data Capture Methods

This study will utilize 2 different web-based platforms, Oncore (Forte Research) for study registration and tracking and REDCap for clinical trial data collection. Both systems are secure web platforms that are compliant with Good Clinical Practices and Federal Rules and Regulations. UW Department of Human Oncology Coordinators will coordinate and manage data collection and entry

Clinical data (including AEs, concomitant medications, and solicited events data) and clinical laboratory data will be entered into the following REDCap. Clinical data will be entered directly from the source documents.

Shadow research charts with original consent forms and documents specifically created for this study will be maintained in the Department of Human Oncology until the study is terminated. The records will then be sent to Wisconsin State Records Archiving facility for long term storage (10 years) and re-archived as needed.

12.2 Confidentiality and Privacy

Subject confidentiality and privacy are strictly held in trust by the participating investigators, their staff, and the sponsor(s) and their agents. This confidentiality is extended to cover testing of biological samples and genetic tests in addition to the clinical information relating to subjects. Therefore, the study protocol, documentation, data, and all other information generated will be held in strict confidence. No information concerning the study or the data will be released to any unauthorized third party without prior written approval of the sponsor.

All research activities will be conducted in as private a setting as possible.

All study staff engaged in the conduct of this project have completed training on the protection of human subjects and the Health Insurance Portability and Accountability (HIPAA) Privacy Rule. In addition, all key personnel (i.e., Principal Investigator, individuals involved in identifying/recruiting subjects, obtaining informed consent, or interacting and intervening with subjects) have undergone Good Clinical Practice (GCP) training.

Information about study subjects will be kept confidential and managed according to HIPAA requirements. All subjects will sign a combined informed consent and HIPAA authorization form that includes specific privacy and confidentiality rights. Study data will be maintained per federal, state, and institutional data policies.

The investigator(s) will ensure that the identities of subjects are protected by using coded subject information. The log of subject identifying information that links subjects to their study-specific identification number will be maintained by the investigator. The log and all study records will be maintained in locked rooms and access will be limited to essential study personnel. The log linking subject code to identifiers will be stored separately from study data. The PI will have access to the log linking code to identifiers, as will authorized study personnel. Electronic study records/files will be stored on a department server and accessed via networked computers that are password-protected with access provided only to authorized study personnel.

Authorized representatives of the following groups may need to review this research as part of their responsibilities to protect research subjects: representatives of the IRB, UWCCC DSMC, UWCCC, authorized personnel of the UW PACT, Other groups at the University of Wisconsin tasked with Research Oversight and compliance, and federal oversight agencies, such as the Food and Drug Administration (FDA).

Records Retention

It is the investigator's responsibility to retain study essential documents for a minimum period of 7 years following completion of the study per UW-Madison institutional policy, or at least 2 years after the last approval of a marketing application in their country and until there are no pending or contemplated marketing applications in their country or at least 2 years have elapsed since the formal discontinuation of clinical development of the investigational product, whichever comes last.

12.3 Retention for Future Research: Data & Biospecimen Banking

Purpose of Storage

The purpose of collecting and storing biospecimens is to establish a biobank for use by UW-Madison researchers to use who are investigating the causes, diagnosis, prevention and treatment of cancer.

Data and/or Biospecimens Being Stored

Blood in a 3 mL standard EDTA tube will be collected from each participant on the day of bone marrow biopsy, and at the 1(for those seen at 1 month), 3, 6, 12, and 24 month follow-ups. This blood will be labeled with a unique subject ID code. All tubes of blood will then be stored in a secure freezer in the secured [name] lab in WIMR.

Saliva will be collected from each participant at the pre-specified timepoints as detailed previously. The saliva will be used for clinical endpoints as detailed previously, any remaining saliva will be stored in an Eppendorf tube in a secure freezer in the secured [name] lab in WIMR.

Location of Storage

Blood and saliva tubes labelled with coded subject ID number, date, and time point, will be stored in the [name] Laboratory. Data associated with the blood and saliva tubes is on a UW password-protected server.

Duration of Storage

Biospecimens will be stored until they are used up in their entirety.

Access to Data, Images, Recordings and/or Biospecimens and Security Measures

UW researchers who are doing biomedical research may apply for access to coded data and blood (no patient identifiers on tube).

Procedures to Release Data or Biospecimens

Researchers must have local IRB approval for their study which will include study of the biospecimens and accompanying data.

Process for Returning Results

There are no plans to disclose results of future testing to research subjects.

Process for Tracking Subject Consent and Authorization

In the consent form for this study, subjects are informed of an optional aspect of the study that involves donating blood for future biomedical research. Subjects are made aware they do not have to donate biospecimens to the Biobank to participate in the study. Subjects must opt into the biobanking aspect of the study by checking a box and initialing a line next to the box.

12.4 Protocol Deviations

A protocol deviation is any noncompliance with the clinical trial protocol or investigational plan requirements. The noncompliance may be either on the part of the subject, the investigator, or the study site staff. Protocol deviations will be assessed for their impact on safety, study operations, and data integrity. Appropriate corrective and preventive actions will be implemented if warranted.

It is the responsibility of the Principal Investigator/site investigator/study staff to use continuous vigilance to identify and report deviations. The Principal Investigator is responsible for assessing whether the deviation constitutes noncompliance as defined by the reviewing IRB and if so, reporting it within the required time frame(s) to the UWCCC and the IRB as applicable

12.5 Publication and Data Sharing Policy

This study will be conducted in accordance with the following publication and data sharing policies and regulations: This study will comply with the NIH Data Sharing Policy and Policy on the Dissemination of NIH-Funded Clinical Trial Information and the Clinical Trials Registration and Results Information Submission rule. As such, this trial will be registered at ClinicalTrials.gov, and results information from this trial will be submitted to ClinicalTrials.gov. In addition, every attempt will be made to publish results in peer-reviewed journals.

13.0 STUDY ANALYSIS

Any deviations from the planned analyses will be described and justified in the final integrated study report. Statistical programming and analyses will be performed using SAS® (SAS Institute Inc., Cary NC), version 9.4 or higher. A formal statistical analysis plan (SAP) will be developed before the database lock. It will include detailed descriptions of summaries and mock-ups of tables, listings, and figures to be included in the clinical study report.

13.1 General Considerations

The statistical analyses in this study will be exploratory since the study is not powered to address any pre-defined statements but to generate valid hypotheses on safety/tolerability, feasibility, and efficacy

issues. A formal sample size calculation was therefore not done. Thus, all resulting p-values and confidence intervals are to be interpreted in the exploratory sense, only.

Data will be appropriately summarized and analyzed using tabulation and graphs for demographic and baseline characteristics, safety and efficacy observations and measurements. Standard descriptive summary statistics (i.e., n, arithmetic mean, standard deviation, median, lower/upper quartiles, and minimum/maximum values) will be calculated for continuous variables. Categorical data will be presented in frequency tables using counts and percentages. For all data collected during the study, listings of the individual raw data will be provided. Individual patient data listings will be presented per parameter.

The main analysis will be performed after the 24-month Follow-up Visit, i.e., when all patients have either completed the visit, are lost to follow-up or have died within this period.

13.2 Determination of Sample Size

Patients in this pilot trial will undergo unilateral gland injection per FDA request. Associated 95% confidence intervals will be provided for the toxicity rate. To describe changes in quality of life or salivary function/composition between baseline and post-injection timepoints, separate one-way ANOVA models will be fit to the data for each measured outcome. After fitting the models to the data, comparisons between the timepoints will be calculated using Tukey's method. Due to the short time frame of intervention, we anticipate that adherence to the intervention will be high (>90% of patients will complete all mandatory study components) and that rates of follow-up will be similarly high (i.e., low rates of drop outs or lost to follow-up).

Interim analysis: In this pilot study, there is not a planned interim analysis.

Sample Size: Six to twelve patients will be accrued, depending on toxicity encountered. If 0/6 or 1/6 participants experience a DLT at Dose Level 0, sample size would be six. If 2/6 participants experience a DLT at Dose Level 0, another cohort would be enrolled at Dose Level -1. Sample size would then be up to 12 patients, unless 2 or more patients at Dose Level -1 experience a DLT, at which point the study would be stopped.

Length of follow-up: Patients are observed for DLT after MSC injection, with a follow-up of 4 weeks after injection. Secondary outcomes will be assessed at 24 months (end of study for patients). DLT is defined as: pain > 5 on a standard pain scale of 0-10 at 1-month after MSC injection OR any serious AE within one-month post-injection (probably or definitely caused by study treatment) or other toxicities described in section 9.7.

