7.0 STUDY DESIGN

7.1 General Design

This single-center, open-label, non-randomized, non-placebo controlled, single-group assignment, pilot study is designed to determine the safety and tolerability of autologous bone marrow-derived MSCs in patients with xerostomia after undergoing radiation therapy for HNC. A total of 6- subjects will be enrolled at UW-Madison for unilateral gland injection (dose level 0). Subject accrual will occur over 0.5 years with the total duration of the trial expected to be approximately 2.5 years.

Following the completion of screening/baseline procedures, and written consent, eligible subjects will undergo bone marrow aspirate in order to obtain MSCs. MSCs will be prepared as described in Section 9.2.

The MSC IMP (dose level 0) will be injected into one submandibular gland under local anesthesia, in the gland that received the lowest radiation dose. Patients with only one submandibular gland will be ineligible. All subjects will be called by a study coordinator 3 days (+/- 2 days) after injection to assess pain and will have a phone visit with a physician 1 week (+/- 2 days) after injection during which the investigator will assess pain and ask about the area of injection regarding redness and/or swelling. All subjects will complete a pain diary with daily entries over the first month to record the occurrence and severity of pain using a 0-10 visual analog scale and occurrence and severity of other adverse events (e.g., redness, swelling, warmth, tenderness, rash, pruritis, nausea, vomiting, fatigue). Patients will also keep a log of all pain medications taken including both narcotic and non-narcotic medications (e.g. ibuprofen, acetaminophen, etc.) for the first month. Subjects will complete 5 follow-up visits over the course of 24 months – at 1, 3, 6, 12, and 24 months following the intervention. Salivary collection for analysis as well as QoL surveys will be obtained at these visits.

Additional Gland Injection: The 6 subjects will be offered optional contralateral submandibular gland MSC injection at dose level 0 upon completion. The primary objective (1 month of follow-up after injection of MSCs) without any DLTs has now occurred.

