11.3 Salivary Flow Rate Assessments

Whole saliva production rates (sialometry) will be measured under unstimulated and stimulated saliva collection conditions, as previously described^{36,37}. Participants will refrain from eating, drinking, and,

smoking for one hour prior to collection. Unstimulated saliva production will be measured first by the passive drool method over a 5-minute time frame. Participants will allow saliva to pool in the mouth and, then, with head tilted forward, gently guide saliva into a saliva collection aid attached to a cryovial. Stimulated saliva production will be measured by having participants chew inert gum base to the pace of a metronome (70 beats per minute) while expectorating saliva (without swallowing) into the saliva collection aid for 5 minutes total³⁸. Cryovials will be weighed before and after collection and the difference in weight (g) will represent the amount of saliva produced in 5 minutes for each condition. Subjects will complete the salivary flow rate assessments at the screening (baseline) visit and at 1-, 3-, 6-, 12-, and 24-month follow-up visits.

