11.4 Salivary Composition Analyses

Salivary composition analyses will focus on qualitative aspects of saliva previously found to change following radiation treatment: salivary pH^{39,40}, total protein concentration (mg/mL)^{41,42}, amylase (mU/mL)^{39,43}, and mucins (MUC5B, mU/mL)^{43,44}. Given that MSCs will be injected into one of the submandibular glands which contain both serous and mucous acinar secretory cells, we will measure products of both types of cells (both= total protein and pH; serous= amylase; mucous= mucins). Salivary pH will be measured using a pH meter (Orion 9810BN, Thermo Scientific). Enzyme-linked immunosorbent assays (ELISAs) will be used to quantify total protein, amylase, and mucin levels. Saliva composition will be assessed on whole saliva samples collected from subjects at each timepoint salivary flow rate is assessed (see Section 11.3). Saliva will be processed, stored at -80C, and analyzed in batch at a later date.

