13.8 Analyses of the Secondary Endpoints

Analyses of the secondary endpoints focus on efficacy of the IMP in the treatment of xerostomia and hyposalivation. All inferential analyses for the secondary outcome variables will be interpreted in the exploratory sense, only.

Patient-reported outcome measures will be evaluated by comparing the changes in salivary QOL from baseline to each follow-up visit and by assessing changes over time, within-group comparisons will be performed with the Wilcoxon signed-rank test.

Salivary flow rate analysis will be analyzed in a manner described by Gronhoj et al. 2018²⁴: by comparing the changes from baseline to each follow-up visit and changes over time, within-group comparisons will be performed with the Wilcoxon signed-rank test.

Salivary composition analyses will focus on qualitative aspects of saliva previously found to change following radiation treatment: salivary pH^{39,40}, total protein concentration (mg/mL)^{41,42}, amylase (mU/mL)^{39,43}, and mucins (MUC5B, mU/mL)^{43,44}. Given that MSCs will be injected into one of the submandibular glands which contain both serous and mucous acinar secretory cells, we will measure products of both types of cells (both= total protein and pH; serous= amylase; mucous= mucins). Salivary pH will be measured using a pH meter (Orion 9810BN, Thermo Scientific). Enzyme-linked immunosorbent assays (ELISAs) will be used to quantify total protein, amylase, and mucin levels. Saliva composition will be assessed on whole saliva samples collected from subjects at the screening visit and the in-person follow-up visits.

To assess the imaging characteristics of submandibular gland after MSC injection, salivary gland size will be measured by ultrasound⁴⁵. Ultrasound imaging is a non-ionizing, noninvasive imaging modality that can be quickly obtained in a standard exam room. Three-dimensional (3D) Bmode data sets will be acquired for tumor volume measurements. If post-RT submandibular glands suppress ultrasound waves to prevent the visualization of the lower outline of the gland, a 2D estimate of gland size will be made.

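### Section 13.2 plans one-way ANOVA with Tukey comparisons on repeated visits of the same subjects and states no subject term; Section 13.8 names a paired test for QoL and flow without saying which analysis leads, and no test for composition

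*Combined protocol and SAP*

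**What the plan says.** Section 13.2, which is headed as the sample-size section, describes change from baseline in QoL and in salivary function and composition. It says that "separate one-way ANOVA models will be fit to the data for each measured outcome" and that "comparisons between the timepoints will be calculated using Tukey's method".

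Section 7.1 describes a single-group study, so timepoint is the only factor. The same subjects supply every level of it. Section 11.3: "Subjects will complete the salivary flow rate assessments at the screening (baseline) visit and at 1-, 3-, 6-, 12-, and 24-month follow-up visits". Section 11.4: "Saliva composition will be assessed on whole saliva samples collected from subjects at each timepoint salivary flow rate is assessed". No subject, random or repeated-measures term appears in Section 13.

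Section 13.8 plans something different for salivary flow: "by comparing the changes from baseline to each follow-up visit and changes over time, within-group comparisons will be performed with the Wilcoxon signed-rank test". It plans the same test for patient-reported outcomes. For composition it lists analytes and assays, then general descriptive statistics, but no test. Neither section refers to the other's method.

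Two statements set the weight of all this. Section 13.1 says "all resulting p-values and confidence intervals are to be interpreted in the exploratory sense, only". Section 13.0 says "A formal statistical analysis plan (SAP) will be developed before the database lock"; that separate plan is not among the documents.

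**The concern.** A one-way ANOVA treats the readings at each visit as coming from different people. Here they come from the same people, so stable differences between subjects stay in the error term and the stated intervals do not match the design. If a repeated-measures ANOVA was meant, the text does not say so.

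For QoL and flow, two methods with different error structures and different multiplicity handling are planned on the same data. The reported result can depend on which one is used. For composition there is no paired alternative. At stake is how readable the efficacy signals from a very small pilot will be.

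**Working it through.** **Figures in the plan.** The documents give no power, effect size, SD or correlation for either method, so there is no figure to reproduce for these analyses.

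**Inputs from the documents.** Six subjects (Sections 7.1 and 8.5); six timepoints, namely baseline and 1, 3, 6, 12 and 24 months (Section 11.3).

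**Assumptions.** Total SD 1 at each visit; equal correlation ρ of 0.3, 0.5 or 0.7 between visits; a shift of 1 SD at all follow-up visits where power is quoted; nominal two-sided 5%.

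**Standard error of a visit difference.**
- One-way ANOVA: √(2/6) = 0.577, whatever ρ is.
- Actual: √(2(1−ρ)/6) = 0.483 / 0.408 / 0.316 at ρ = 0.3 / 0.5 / 0.7.
- Ratio: 1/√(1−ρ) = 1.20 / 1.41 / 1.83.

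**Error degrees of freedom.** One-way: 6 × 5 = 30. With a subject term: 5 × 5 = 25. Tukey family with six timepoints: 6 × 5 / 2 = 15 pairs.

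**Simulation (200,000 trials per setting).**

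| | ρ = 0.3 | ρ = 0.5 | ρ = 0.7 |
|---|---|---|---|
| One-way F, type I error | 1.5% | 0.5% | 0.1% |
| Coverage of nominal 95% one-way interval, unadjusted | 97.7% | 98.9% | 99.7% |
| One visit against baseline, unadjusted power: one-way | 38% | 37% | 37% |
| Same, subject term added | 51% | 65% | 86% |
| Same contrast, Tukey over 15 pairs: one-way | 9% | 8% | 7.5% |
| Same, subject term added | 18% | 29% | 54% |
| Signed-rank, unadjusted | 26% | 35% | 54% |
| Paired t (5 df), unadjusted | 39% | 51% | 72% |

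With a subject term the overall F-test holds about 5% type I error at all three correlations.

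**Do the two planned methods agree?** At ρ = 0.7 the planned Tukey comparison flags the 1-SD shift in about 7.5% of trials and the signed-rank test in about 54%. Part of that gap is multiplicity, since Tukey adjusts over 15 pairs and the signed-rank test is unadjusted.

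**If correlation fades with time.** Under AR(1) by visit order at ρ = 0.5 (visits treated as equally spaced), the nominal 95% one-way interval covers 99.1% for baseline to 1 month and 94.8% for baseline to 24 months. An ANOVA with a subject term that assumes equal correlation then has about 7% type I error for the F-test and about 9% for baseline to 24 months.

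**Limits of the signed-rank test.** The smallest two-sided p is 2/2⁶ = 0.031 with six subjects and 2/2⁵ = 0.0625 with five. The first Holm step over two contrasts needs 0.05/2 = 0.025, which 0.031 cannot meet.

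**The case against.** The case for leaving the text alone is reasonable. The ANOVA sentence sits in the sample-size section and is introduced as descriptive. Section 13.8 is the secondary-endpoint section and already plans paired tests for QoL and flow. All p-values are exploratory, individual data will be listed, and the later SAP could settle the choice. The Tukey procedure is also the only multiplicity-adjusted method planned for these outcomes. Most of this stands, and it keeps the severity low. It does not resolve which method leads or give composition a paired analysis, and Section 13.0 does not say that the SAP will choose between the two.

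It can also be argued that pairing buys nothing at low correlation, since the paired t and the one-way contrast have almost equal power at ρ = 0.3 (39% against 38%). That comparison mixes the gain from pairing with a drop from 30 to 5 error degrees of freedom. Adding only the subject term moves power from 38% to 51%. Under AR(1) at ρ = 0.5, however, the paired t and signed-rank tests do worse than the unadjusted one-way contrast at 24 months (30% and 20% against 39%).

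A reader might infer that ignoring the repeated measures produces spurious significance. The calculations do not support that: with positive correlation the planned analysis errs on the cautious side or is close to nominal. A reader might also infer that composition has no analysis. It does, through Section 13.2 and descriptive summaries; what it lacks is a paired one.

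**Conclusion.** The point holds, with minor impact. As written, Section 13.2 applies a model for independent groups to repeated visits of the same subjects. Section 13.8 names a paired test for QoL and flow with no stated precedence, and composition is left with the unpaired model as its only inferential method. Under equal positive correlation the consequence is intervals that are too wide and lost power.

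The direction needs only positive correlation between visits. The sizes rest on the assumed correlations, the assumed 1-SD shift and n = 6. The DLT endpoint, the dose decision and the drop-out-based feasibility assessment do not use these tests, and nothing here should be read as questioning them.

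**What to change.** Replace the one-way ANOVA in Section 13.2 with one within-subject analysis covering QoL, flow and composition, and state in Section 13.8 which analysis leads. Either choice is acceptable if named in advance:

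- **(a)** The signed-rank test already planned, on visit-minus-baseline changes, extended to composition and reported as unadjusted and exploratory with paired estimates and intervals.
- **(b)** A repeated-measures model with a subject term that does not rely on equal correlation between visits.

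Say whether contrasts are adjusted for multiplicity.

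The protocol cost is a few sentences and a few lines of SAS. Option (a) has real downsides at this size. It cannot survive multiplicity adjustment, and with one subject missing it cannot reach 5%. At ρ = 0.3 it has less unadjusted power than the one-way contrast (26% against 38%). Its exact interval at n = 6 is simply the range of the six changes (coverage 1 − 2/64 = 96.9%). A paired t estimate reported alongside has only 5 degrees of freedom and assumes roughly normal changes. For option (b), the AR(1) results above are the reason not to settle for an equal-correlation model.

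Two related clarifications belong in the same edit. Section 7.1 says "The 6 subjects will be offered optional contralateral submandibular gland MSC injection at dose level 0 upon completion". The sub-study has its own calendar in Section 10.1, but Section 13 should state whether main-study visits that fall after a second injection enter the baseline contrasts. As a side point, Section 11.2 lists QoL at baseline, 3 and 6 months, with 1 month only for a dose-escalation cohort that this pilot does not define. The synopsis and Sections 6.0, 9.13 and 10.1 give 1, 3, 6, 12 and 24 months. These lists need reconciling, since they set the number of QoL contrasts.
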